## 1.2 Investigational Agent

The investigational product is autologous mononuclear cells (MNC) derived from umbilical cord blood (UCB) with minimal *ex vivo* manipulations. The delivery vehicle contains a cryoprotectant solution of 10% dimethyl sulfoxide.

## 1.3 Preclinical Data

Preclinical studies were conducted under this IND to comply with the recommendations received from the FDA during our pre-IND meeting (Dec 2, 2011) and subsequent correspondence (Feb 23, 2011). The pre-clinical investigations were predicated on a two-tiered approach that utilized large animals for autologous cell testing and small animals for human cell testing. The feasibility of the collection, manufacturing, and delivery components employed in prior pre-clinical and clinical studies has been demonstrated. The small animal testing utilized an immune-deficient rodent model system to determine the dose-dependent toxicology and efficacy of human-derived umbilical cord blood product that was manufactured and administered in the same manner as

conducted for the Phase I study and will be conducted for this Phase II study. Pre-clinical safety and efficacy testing is ongoing in large animal studies to provide ongoing learning and optimization of various aspects of the clinical development for this product.

**Preclinical Data Summary-** Initially, three dedicated preclinical studies were designed and executed to address the specific questions required to determine the risk/benefit analysis for the proposed Phase I human study. The pre-clinical studies demonstrated that intramyocardial delivery of the umbilical cord blood-derived product does not cause any clinically significant adverse reactions throughout follow-up after intramyocardial injection of umbilical cord blood derived MNC compared to a placebo control cohort as measured by cardiovascular surrogate markers as well as clinical morbidity and mortality. The safety of the dose was confirmed in this large animal model in parallel to the confirmed safety profile of even higher doses as tested in a rodent model system. Finally, the benefits of human umbilical cord blood-derived mononuclear cells as manufactured in the GMP facility at Mayo Clinic for these three pre-clinical studies were demonstrated in a pressure overloaded right ventricular animal model system as: improved cardiac structure, reversal of pathological gene expression profiles, and prevention of fibrotic changes upon histology analysis. Collectively, these original preclinical studies suggested a safe and effective dose of umbilical cord blood-derived mononuclear cells with intramyocardial delivery into the right ventricle [12].

Double-blinded, randomized, placebo-controlled studies are continuously performed in large animals using autologous UCB derived products at Mayo Clinic as part of product development. Ongoing pre-clinical studies have not identified any new or unexpected safety concerns of the product and delivery strategy. These ongoing studies continue to utilize a pulmonary artery banded piglet that aims to model the right ventricular stress of an age-matched patient undergoing Stage II surgical repair. The autologous UCB-MNC product is equivalent to our clinical product. The randomized and blinded studies have continued to demonstrate a favorable safety profile (lack of bleeding, arrhythmia, tumor formation, ventricular damage) of this product and the delivery procedure technique that is used within the Phase I clinical protocol [13]. A surrogate marker of efficacy that has recently demonstrated the most significant improvement has been the increased cardiac proliferation in the right ventricle following cell delivery (publication pending). Of note, improved ejection fraction in the right ventricle of this model has not been demonstrated in these preclinical studies as the source of cardiac stress is a surgically induced. Fixed narrowing of the outflow track of the pulmonary artery limits the ability to effectively measure change in cardiac function irrespective of any meaningful regenerative response to cell therapy. This permanent obstruction to outflow in these animal studies does not recapitulate the HLHS condition in humans and thus we have begun using this animal model system to characterize the mechanism of action at the molecular level. Of note, the increased cardiac proliferation of the right ventricle would indeed contribute to the increased cardiac mass needed for optimal functioning of the systemic right ventricle.

Thus, this product and product delivery procedure technique continues to demonstrate a favorable safety profile in the large animal model system without evidence of worsening arrhythmia, bleeding, cardiac dysfunction, or tumor formation at the time of and following cell

therapy. Furthermore, cardiac proliferation is directly attributable to cell therapy and this molecular mechanism is expected to contribute to long-term cardiac benefit.

#### 1.4 Clinical Data to Date

The following is a summary of available data through May 17, 2018 for safety, feasibility, and efficacy from the first ten treated subjects enrolled in the Phase I study and the first three subjects enrolled and accrued in the concurrent observational control study.

#### Feasibility Experience in Phase I Study (IND 15343)

The clinical feasibility of this study design has been demonstrated without modifications to the original version of the Phase I protocol in the context of cell product manufacturing, method of delivering the cell product, or any changes recommended by the DSMB. As HLHS is rare, the inclusion and exclusion criteria were modified to achieve enough enrollment in a more reasonable time. The most significant change that improved feasibility was modifying the exclusion criterion pertaining to subjects being on mechanical cardio-pulmonary support such as ECMO. There were several patients that were pre-screened for the study that received ECMO support following Stage I surgery for reasons unrelated to cardiac dysfunction, and thus it was inappropriate to exclude those patients by assuming that they would be higher risk from a cardiac standpoint. The AE definition and reporting criteria were also modified after the second treated subject as the requirement to report all AEs for this subject population is challenging due to the frequent occurrence of expected events in this critically ill population, resulting from the Stage II standard of care procedure and the underlying HLHS congenital heart disease. Thus, the purpose of the modification to the AE definition and reporting criteria was to allow investigational sites to focus on the reporting of the more critical AEs given the clinical context of this unique subject population.

In the context of the feasibility of UCB collection and manufacturing, the study protocol and manufacturing SOPs ensure a high yield of available products to clinical sites for investigational cell therapy under this IND in subjects that participated in the UCB Collection Study. From the 98 consented patients that intended to undergo umbilical cord blood collection as participants in the Mayo Clinic UCB Collection Study, 80 patients had umbilical cord blood collected and received by the manufacturer. The 18% failure to collect/manufacture a UCB-derived product was most commonly related to mothers delivering early or mothers consenting too late, which affected the feasibility of the logistics. The majority of UCB collection failures have not been related to technical problems in the past 12 months as these have been effectively addressed with improvements in training of staff involved in UCB collections and manufacturing SOP refinements. The UCB collection failure rate will be further reduced with dedicated UCB training within the Phase IIb clinical sites. During the Phase I Study, on December 1, 2016, the product manufacturing was transitioned to a partnering CMO, ReGen Theranostics (Rochester, MN). Manufacturing of the last 40 products as of March 2018 at ReGen have resulted in 37 products available for release (92% success rate). The three products that were not made available for release were due to 1) a manufacturing error that was an unacceptable quality control issue, 2) a critical labeling issue between collection and manufacturing that was not able to be reasonably resolved, and 3) a low cell recovery linked to a low collection volume that

limited the manufacturing yield of that product. The manufacturing and UCB collection logistics have been refined such that they will be unlikely to limit enrollment and treatment in the Phase IIb study.

The feasibility of the Phase I study was most significantly compromised by the study inclusion and exclusion criteria. One in every six acceptable autologous products was administered during the Stage II surgery based largely on the narrow Phase I study eligibility criteria. The Phase IIb study has been designed to address the feasibility issue identified in Phase I by requiring fewer exclusion criteria for subject enrollment. It is anticipated that one out of every two subjects with manufactured autologous product will be eligible for enrollment in the treatment arm of this Phase IIb study. Therefore, treating up to fifty subjects under this Phase IIb study should be feasible within a 5-7 site clinical trial.

The feasibility of the Observational study that required prospective data collection for control subjects proved to be highly problematic as recruitment was limited to only three subjects in this time period. The primary limitation to recruitment was in part the bias for eligible subjects to choose to participate in the treatment study. Only a few subjects that met all eligibility criteria and had available UCB product decided to not participate in the Phase I cell-delivery study. Additionally, a significant number of subjects that did not have available autologous product and met all eligibility criteria of the Observational study were unwilling to participate in the Observational study that required multiple non-standard of care clinical visits with additional blood and imaging studies. Therefore, the Phase IIb study was designed with fewer non-standard of care clinical visits to address the feasibility of recruiting a proper control cohort.

### **Safety and Efficacy Experience in Phase I Study (IND 15343)**

In the context of safety, adverse event reporting and data comparison across the small sample size has informed most changes between the Phase I and Phase II protocols, especially given the highly complex and individualized clinical care that these patients undergo. As previously reported to the FDA, the adverse event reporting criteria was modified in protocol amendments to allow investigational sites to focus on the reporting of the more clinically relevant AEs given the clinical context of this unique subject population. We have utilized this Phase II protocol for reporting the current Phase I study clinical data for all treated subjects as of the May 17, 2018 cut-off date. There were no SAEs classified with a “definite,” “probable,” or “possible” relationship to the product or product delivery. The Sponsor has adjudicated all SAEs and the DSMB has systematically reviewed all these SAEs. Of these 27 SAEs, one treated subject experienced 15 SAEs and another treated subject experienced 7 SAEs over the course of a complicated, multi-factorial sequence of events, which were all classified as not related to the product or the product delivery. Of note, there was a single non-serious AE that was classified as having a “definite” relationship to the product delivery. This was due to slight bleeding at the site of one injection during cell delivery that was controlled by the placement of a suture. This first-in-child study has been achieved without definitive safety concerns in terms of events such as arrhythmias, bleeding, cardiac damage, or tumor formation that were considered potential risks of the cell product and its delivery procedure (see Section 1.5).

The subjects in the Phase I study will continue to be followed according to the existing Phase I protocol. New subjects, both treatment and control, will be enrolled in the Phase IIb study while enrollment in the Phase I and Observational studies are simultaneously discontinued. Enrollment closure in the Phase I and Observational studies will be closed at each investigational site at the time that corresponding site is approved to enroll in the Phase IIb study.

### **1.5 Dose Rationale and Risks/Benefits (Treatment arm only)**

The target dose of the investigational agent is 1-3 million TNC per kg body weight divided into multiple injections of 0.1 mL from a thawed product containing 10-30 million TNC cells per mL. The dose of this cell-based product was originally determined according to clinical experience in adult clinical trials, our pre-clinical safety studies, and now our Phase I clinical study.

**Dose Comparison-** Other clinical trials have used a range of  $10^6$ - $10^8$  TNC delivered in chronic ischemic adult hearts in divided doses of 0.2 to 0.5 mL per injection with a total volume of 2-20 mL of solution. (*Thus, an analogous example based on our dose for a 70 kg adult would be 210 million cells in 7 mL of 30 million cells/mL in 14 injections of 0.5 mL each.*) Therefore, we aimed to keep the concentration of cells comparable to the adult experience, recognizing that total volume of injected cells, volume of each injection and total dose of cells were equally important considerations.

**Delivery Approach-** Intramyocardial injections of UCB-MNC and subsequent follow-up was conducted in both small and large animal models to determine feasibility, safety, and efficacy of cell delivery. The rationale for intramyocardial delivery through direct injections from the epicardial surface for this cell-based product was chosen based on minimizing the risk of cell delivery for single ventricle patients. Because these patients are required to undergo open chest cardiac surgery, the epicardial surface is routinely exposed and intramyocardial delivery at the time of surgery as an “add-on” was determined to be less invasive and less risky compared to intracoronary infusion which would require a separate catheter-based procedure and its associated ionizing radiation.

Children undergoing Stage II surgery will most likely be less than 10 kg and thus will require not more than 1.0 mL of frozen product to achieve the full target dose. The ability to collect and process this concentration of human cell-based product from umbilical cord blood was determined to be reproducible in preclinical studies and in our Phase I clinical study. The ability to “thaw and deliver” without requiring individual dosing of the cell product is meant to reduce the risk of product calculation errors and mixing errors at the bedside. The amount of dimethyl sulfoxide (DMSO) delivered in small volume stocks is considerably lower than in established clinical applications such as bone marrow derived stem cells for hematopoietic applications.

**Dose/Delivery Toxicity Experimentations-** We empirically tested for toxicity in an intramyocardial dose escalation preclinical study to determine potential risk of tumor formation, arrhythmias, and decrease in cardiac structure/function due to possible damage to blood supply. We also completed a double-blinded, randomized study using autologous umbilical cord blood derived MNC in a size-matched porcine cohort for long-term safety using the same dosage of 3

million cells per kg of body weight and intramyocardial delivery procedure technique as used in the Phase I study. These potential risks are based on literature review and expert experience and not informed based on any specific data obtained in our studies. No clinically significant adverse reactions occurred in these preclinical studies, as described in Section 1.3 above.

Additionally, the Phase I clinical study, up to the time of the data cut-off, did not result in any SAEs that were classified as having a “definite,” “probable,” or “possible” relationship to the cell therapy product or to its delivery procedure.

**Risks of Autologous UCB-MNC Product and Intramyocardial Delivery Procedure-**

The clinical experience up to the time of data cut off has been reported in Section 1.4. The clinical experience has highlighted a single AE with minor bleeding that was definitively related to product delivery. The theoretical risks (in addition to risk of bleeding) that will continue to be closely monitored for in this protocol include:

- Mild ventricular tachycardia and/or other mild ventricular arrhythmias
- Mild myocarditis
- Mild pericarditis
- Mild to moderate myocardial infarction
- Mild to moderate pericardial effusion
- Mild to moderate fever for up to 3 days following cell delivery
- Mild to moderate bleeding at the injection site

**Benefits of Autologous UCB-MNC Intramyocardial Delivery-** The potential benefits of autologous UCB-MNC are derived from pre-clinical studies and preliminary follow-up data from the current Phase I clinical study, suggesting that benefits of the UCB-MNC and its delivery procedure may improve and/or sustain cardiac function within the first 3-months after Stage II surgery.

## 2 STUDY OBJECTIVES

The purpose of this Phase IIb clinical study is to evaluate the efficacy and safety of autologous UCB-MNC intramyocardial injections into the single, morphological right ventricle of subjects with HLHS or HLHS variants requiring Stage II surgical repair. Thirty to fifty treated subjects and thirty to fifty control subjects will be accrued. Subjects accrued in the treatment arm (Arm A) of this study will be treated with a single dose following successful completion of Stage II surgical repair. Subjects accrued in the control arm (Arm B) of this study will be followed according to the same protocol requirements as the treatment arm but will not receive cell therapy. In the treatment and control arms, surrogate markers of cardiac function, growth, success in reaching Stage III surgical repair pre-operative work-up, time to cardiac transplantation or death, and cumulative days of hospitalization will be recorded and evaluated following the completion of Stage II surgery for up to four years, or until the pre-operative work-up for the Stage III surgical repair has been completed or until cardiac transplant, whichever is first. Development and quality of life as measured by questionnaires will also be monitored. Follow-up surrogate markers and the other variables noted above that are recorded for this study will be compared to baseline and by study arm. The surrogate markers and other variables are described in Section 3 of this protocol.

The objective is to evaluate the short-term (up through 3 months post-Stage II surgical repair) cardiac function, growth, and cumulative days of hospitalization following discharge for the Stage II surgical repair in the treatment and control arms, adjusting for baseline.

This evaluation will also include long-term (6 months and up to 4 years post-Stage II surgical repair or until the pre-operative work-up for the Stage III surgical repair has been completed or until cardiac transplant), cardiac function, growth, ability to reach Stage III surgical repair pre-operative work-up and time to cardiac transplantation or death in the treatment and control arms, adjusting for baseline.

As part of a sub-group analysis, the images collected at 3-months post-Stage II surgery will provide a stand-alone analysis to test the hypothesis that MRI provides a more sensitive measure of sub-clinical cardiac dysfunction, pulmonary artery size, and patency of the surgical anastomoses. It is anticipated that nearly 10% of HLHS and HLHS variant patients may have actionable findings detected by MRI at 3 months post-Stage II surgery that would have been otherwise undetected with a standard of care echocardiogram. This sub-group analysis could provide the evidence to establish a new standard of care following Stage II surgery.

## 3 STUDY DESIGN

### 3.1 General Design

This Phase IIb study is a multicenter, prospective, open-label, non-randomized, observational study designed to evaluate the efficacy and safety of UCB-MNC delivered into the right ventricular myocardium of subjects with HLHS or HLHS variants with right ventricular dependent single ventricular CHD at the time of a planned Stage II surgical repair. This will be achieved by comparing the data collected in the treatment group (Arm A) to the equivalent data collected in the control group (Arm B), adjusting for baseline.

The concurrent control arm (Arm B) must meet identical study eligibility criteria as the treatment arm (Arm A), except for the requirements related to UCB-MNC product acceptability and DMSO sensitivity. The control arm will undergo the same planned Stage II surgical repair without the investigational cell delivery add-on procedure and will follow-up post-surgery in the same manner as the treatment arm (see Section 6 of this protocol).

#### 3.1.1 Treatment Assignment

[figure not shown]
When possible, prior to enrollment in this study, expecting parent(s) with prenatal diagnosis of HLHS or HLHS variants will be offered enrollment in a separate, ongoing Umbilical Cord Blood Collection Study for the collection of UCB. The parent(s) and/or legal guardian(s) may be consented to allow their child to participate in the treatment group (Arm A) of this clinical study if the patient requires Stage II surgical repair, if the autologous UCB-MNC manufactured product is determined to be acceptable for release to the investigational site for clinical use, and if the subject meets all other eligibility criteria for this study. Patients without frozen UCB-MNC product or without UCB-MNC product determined to be acceptable for clinical use in this study may be consented to the control arm of this clinical study if the subject meets all non-treatment-only eligibility criteria for this study.

#### 3.1.2 Subject Evaluation

Once consent has been obtained, subjects will enter the screening phase where a pre-operative baseline work-up will be performed as outlined in Section 6 of this protocol. Following the pre-operative work-up, Stage II surgical repair, and final eligibility confirmation according to the inclusion and exclusion criteria listed in Section 4 of this protocol, the subject will be enrolled on to the trial. Following Stage II surgical repair hospitalization, subjects will enter active follow-up. This includes evaluation in-clinic at 3 and 12-months post-Stage II surgical repair, which will include the collection of imaging data. Phone follow-ups will be conducted at 1 month and 6 months post-Stage II surgery and conducted every 6 months following the 12-month in-clinic visit up to pre-operative work-up for the Stage III Fontan palliative surgery, cardiac transplant or to 4 years post-Stage II surgery, whichever is first.

### 3.1.3 Study Schema

The overall study participant flow chart for this study is shown below.

### 3.2 Short Term Endpoints

The primary short-term efficacy endpoint regarding the cell product and its delivery procedure is:

Change in right ventricular cardiac function at 3 months post-Stage II surgery compared to baseline, measured by *apical fractional area change, circumferential strain, and longitudinal strain on echocardiogram*.

Secondary short-term efficacy and safety endpoints in order of their relevance and importance in this clinical study are:

- 1) Change in cardiac function between baseline and hospital discharge for Stage II surgery, measured by echocardiogram.
- 2) Cumulative days of hospitalization per patient at 1 and 3-months post Stage II surgery.
- 3) Change in weight, heart rate, and oxygen saturation at 3-months post Stage II surgery compared to baseline.

Additional variables may be assessed in an exploratory manner.

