Reference therapy	Control cohort of 30-50 subjects, enrolled in the control arm of this study, not receiving the cell product, which will be enrolled and followed using the inclusion/exclusion criteria and follow-up requirements outlined herein.
Treatment Assignment	When possible, prior to enrollment in this study, expecting parent(s) with the prenatal diagnosis of HLHS or HLHS variants will be offered enrollment in a separate protocol for the collection of UCB. The collected UCB will be used for UCB-MNC treatment described herein if the subject is enrolled in and meets all eligibility criteria for this open-label study, and if the UCB-MNC manufactured product is determined to be acceptable for release to the investigational site for clinical use. Subjects without frozen UCB-MNC product available or with frozen UCB-MNC that is NOT acceptable for clinical use, or that choose not to participate in the treatment arm may be enrolled in the control arm of this study.
Primary and Secondary Short-Term Endpoints	
The primary short-term efficacy endpoint regarding the cell product and its delivery procedure is:
 
Change in right ventricular cardiac function at 3 months post-Stage II surgery compared to baseline, measured by apical fractional area change (FAC), circumferential strain, and longitudinal strain all as determined by echocardiography.
 
Secondary short-term safety and efficacy outcomes in order of their relevance and importance in this clinical study are:
 
 
1) Change in right ventricular cardiac function between baseline and hospital discharge for Stage II surgery, measured by echocardiogram.
 
2) Cumulative days of hospitalization per patient at 1 and 3-months post Stage II surgery.
 
3) Change in weight, heart rate, and oxygen saturation at 3-months post Stage II surgery compared to baseline.
 

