Primary and Secondary Long-Term Endpoints	
The primary long-term efficacy endpoint regarding the cell product and its delivery procedure is:
 
Change in right ventricular cardiac function at 12 months post-Stage II surgery compared to baseline, measured by echocardiogram.
 
Secondary long-term safety and efficacy endpoints in their order of relevance and importance in this clinical study are:
 
 
1) Change in weight every 6 months post-Stage II surgery compared to baseline.
 
2) Change in heart failure medication taken every 6 months post-Stage II surgery compared to baseline.
 
3) Change in arrhythmia medication taken every 6 months post-Stage II surgery compared to baseline.
 
4) Success of subject being scheduled for Stage III surgical repair.
 
5) Time (days) until listed for cardiac transplantation, or death following the 6-month follow-up.
 
6) Change in right ventricular function at Stage III surgery pre-op work-up compared to baseline, obtained by echocardiogram and cardiac catheterization.
 

Statistical Methodology	
Quantitative outcomes, like FAC, at specified time post-surgery, will be analyzed using analysis of covariance to estimate the difference in means between the cell-based therapy and control groups after adjusting for the baseline value (the measured value of the same variable, e.g. FAC, at the time of Stage II surgery). Categorical outcomes, like able to undergo Stage III palliation surgery, will be compared between groups using a chi-square test. Time-to event outcomes, like time until listing for cardiac transplant, will be compared using the Kaplan-Meier method and log-rank test. We will similarly do analyses of other variables based upon this patient subset. In secondary analyses we will also fit models which allow the treatment effect (mean difference between the cell-therapy group control groups) to depend on baseline cardiac function measures or other baseline values. This will be done by using the linear, logistic and Cox regression models as appropriate.

Imaging Core Lab	
M. [name] (Core Lab Director) Mayo Clinic Pediatric and Adolescent Medicine [name] [name]

Contract Manufacturing Organization	
ReGen Theranostics, Inc. [name] [name]

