## 7 STATISTICAL ANALYSIS PLAN

Sections 3.2 and 3.3 of this protocol provide a full description of the study endpoints.

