### 7.1 Sample Size Determination

Sample size calculations were performed using alpha = 0.05 and assume equal variance across study arms. With 50 subjects per arm we will have 80% power to detect an effect size as small as 0.57 in difference in cardiac function measures. This is built on the assumption all subjects from both arms have complete data at baseline and 3-month follow-up visits. In the event of attrition or incomplete data in 40% of participants, equal across study arms, the study has 80% power to detect an effect size as small as 0.74 in difference in cardiac function measures.

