#### Multiplicity

For both the primary analyses of short-term outcomes and the secondary analysis of long-term analyses, there will be one primary (or first) analysis and thus no correction will be made for multiple comparisons. A sequence of outcomes of interest is also given (Sections 3.2 and 3.3) for each of the short and long-term outcomes, and significance will be assessed in the order of these sequences. Therefore, no adjustment is made for multiple testing.

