### 7.4.3 Short Term Efficacy Analysis

#### Primary Outcome

The primary analysis of the primary outcome apical fractional area change 3 months post Stage II palliative surgery will be done using analysis of covariance (ANCOVA), including a model term for the difference in means between the cell-based therapy and control groups, as well as a model term for apical fractional area change at time of surgery to account for subject baseline condition. In secondary analyses of the primary outcome we will, using interaction terms, fit a model allowing the treatment effect (mean difference between the cell-therapy and control groups) to depend on baseline fractional area change.

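### The summary and Section 3.2 name three primary echo measures with no decision rule while Section 7.4.3 tests FAC alone, and the ordered testing in Section 7.3 states no stop.

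*Combined protocol and SAP*

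**What the plan says.** **Endpoint text.** Section 3.2 defines the primary short-term endpoint as the change from baseline to 3 months in right ventricular function, measured by "apical fractional area change, circumferential strain, and longitudinal strain on echocardiogram". The Clinical Study Summary agrees: "measured by apical fractional area change (FAC), circumferential strain, and longitudinal strain all as determined by echocardiography". Neither gives an any, all or composite rule. Section 7 opens by deferring to these definitions: "Sections 3.2 and 3.3 of this protocol provide a full description of the study endpoints".

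**Analysis text.** Section 7.4.3 begins "The primary analysis of the primary outcome apical fractional area change 3 months post Stage II palliative surgery" and specifies an ANCOVA with baseline FAC as covariate. Section 7.4.4 does the same at 12 months, although Section 3.3 names no echo measure for that time point. The summary's statistics row also takes FAC as its example: "Quantitative outcomes, like FAC, at specified time post-surgery, will be analyzed using analysis of covariance". Strain is not mentioned in Section 7.

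**Multiplicity text (Section 7.3).** For the primaries, "there will be one primary (or first) analysis and thus no correction will be made for multiple comparisons". For the listed outcomes, "significance will be assessed in the order of these sequences. Therefore, no adjustment is made for multiple testing".

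**Sizing text (Section 7.1).** With 50 per arm, "80% power to detect an effect size as small as 0.57 in difference in cardiac function measures". With 40% incomplete data the corresponding effect is 0.74. The measure is not named.

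**The concern.** Section 7 calls Section 3.2 the full description of the endpoints, so its three-measure wording cannot be set aside as background. If strain is significant and FAC is not, a reader of Section 3.2 could claim that the primary endpoint was met, while a reader of Section 7.4.3 would say that it was not. The plan should exclude that choice before the data are seen, all the more in an open-label, non-randomized study.

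The second part concerns the endpoints below the primary. A fixed order protects the error rate only if testing stops at the first non-significant result and each step is a single test. Section 7.3 states the order and draws the conclusion without stating the stop. Several steps are bundles: hospital days at 1 and at 3 months; weight, heart rate and oxygen saturation; weight every 6 months. Nothing says what passing such a step means.

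**Working it through.** **Inputs.** From Section 7.1: alpha 0.05, 50 per arm, effect 0.57; with 40% incomplete, 30 per arm and 0.74. From Section 3.2: three primary measures and three secondary steps. The correlations ρ between tests are not in the documents. I assume one common value and vary it from 0 to 0.9.

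**1. The plan's own figures.** Two-sample t test, two-sided 0.05, noncentrality d·√(n/2):
- d = 0.57, n = 50: 0.57 × √25 = 2.85, power 80.6%. Smallest d at 80% power: 0.566.
- d = 0.74, n = 30: 0.74 × √15 = 2.87, power 80.5%. Smallest d: 0.736.

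Both stated effects reproduce. They describe one test at 0.05, which fits FAC as sole primary.

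**2. At least one of k tests significant under the null.** For ρ = 0 this is 1 − 0.95^k. In general it is 1 − ∫ φ(x)·[Φ((1.96 − √ρ·x)/√(1−ρ)) − Φ((−1.96 − √ρ·x)/√(1−ρ))]^k dx.

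| Tests | ρ=0 | 0.3 | 0.5 | 0.7 | 0.9 |
|---|---|---|---|---|---|
| 3 (FAC and two strains) | 14.3% | 13.6% | 12.5% | 10.9% | 8.4% |
| 4 (short-term steps as single tests) | 18.5% | 17.4% | 15.6% | 13.0% | 9.4% |
| 7 (steps split: 1 + 1 + 2 + 3) | 30.2% | 27.2% | 23.0% | 17.8% | 11.4% |

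**3. FAC null but a strain measure significant, no true effect.** Row one minus the 5% in which FAC itself is significant: 14.3 − 5 = 9.3% at ρ = 0, 12.5 − 5 = 7.5% at 0.5, 8.4 − 5 = 3.4% at 0.9. This counts significance in either direction, so it is an upper limit for a false claim of benefit.

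**4. If all three measures were meant as primary.**
- Any of three, Bonferroni: alpha 0.05/3 = 0.0167. The detectable effect with 50 per arm rises from 0.57 to 0.66.
- All three required: no alpha correction is needed. By simulated unadjusted t tests, power at 0.57 on each measure is about 52% (ρ = 0), 62% (0.5) and 73% (0.9).
- The planned analysis is ANCOVA, and Section 7.1 does not say whether 0.57 is in raw or residual SD units. If raw, and with an assumed baseline correlation of 0.5, the effective size is 0.57/√(1 − 0.25) = 0.66. Single-test power is then 90% and all-three power about 74% to 85%.

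All figures are for a single look. The interim analyses in Section 7.4.1 are a separate matter.

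**The case against.** The best reply is that the primary test is already fixed. Section 7.4.3 names FAC with its model and covariate, Section 7.4.4 repeats it, and Section 7.3 speaks of one primary analysis. Appendix B gives tracing rules for FAC, and its text does not mention strain. This is convincing about intent. A reader might infer that the primary analysis is undefined, or that the trial runs at a 14% error rate. The documents support neither: that figure needs an any-of-three rule that no section states, together with independent echo measures of the same ventricle. What stands is narrower: the endpoint definition is broader than the analysis, and Section 7 endorses that definition.

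Secondly, concluding that no adjustment is needed from the order makes sense only as fixed-sequence testing, so a stop is nearly implied. I accept that as the probable intent. It still does not say how a bundled step passes. Nor should the 30% in the table be taken as an estimate: hospital days at 3 months include those at 1 month, so zero correlation is impossible for that pair. It is an upper bound.

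Thirdly, Section 3.3 does not contradict Section 7.4.4. It names no competing measure, and the later section simply specifies one. Naming FAC there is for consistency only.

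Finally, this is a Phase IIb study meant to inform later definitive trials. That limits the consequences but does not remove the ambiguity.

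**Conclusion.** The point holds as an inconsistency between endpoint and analysis, and as an incomplete testing procedure. It should be corrected. If FAC is the sole primary, as Section 7 and Appendix B indicate, nothing is wrong with the stated 5% error and 80% power at a single look. The exposure is the freedom to turn to strain when FAC fails, worth up to about 3% to 9% of trials under no effect. For the ordered list, order alone does not justify making no adjustment. Without a stop the chance of at least one false positive is about 9% to 19% over four single-test steps, and higher as an upper bound if bundled steps are split. These ranges rest on an assumed common correlation between 0 and 0.9. The finding that the texts differ and that no stop is stated rests on no assumption.

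**What to change.** 1. In the Clinical Study Summary and Section 3.2, name 3-month apical FAC as the single primary short-term endpoint. For consistency, name 12-month FAC in Section 3.3.
2. List circumferential and longitudinal strain either as ranked secondary endpoints, in an order set by the sponsor, or as descriptive.
3. In Section 7.3, treat the short-term and long-term lists as two families. Within each, state that efficacy testing follows the listed order, with one named variable and time point per step or a stated rule for passing a multi-test step. Testing uses the significance level that applies to that analysis, which leaves room for whatever is decided about the interim looks. It stops at the first non-significant result, and later efficacy results are descriptive.
4. Report safety comparisons, such as arrhythmia medication (treated as safety in Section 7.4.5), outside the sequence so that an earlier efficacy result cannot gate them.
5. If the sponsor does intend all three measures as primary, state the any or all rule with the matching alpha or power from step 4 of the working.

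The cost is wording in four places plus a sponsor decision on strain and on the order inside bundled steps. There are no new data, and no sample-size change if FAC is the sole primary. The downside is real: strain can no longer carry the primary claim, and lower-ranked efficacy items, including transplant listing or death in the Section 3.3 list, may end up descriptive only.
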